#### 7.1.2 Secondary Objectives

# 7.1.2.1 To compare diagnostic accuracy of F-R infusion imaging technique to low MI bolus imaging technique.

The proposed tests with sample size 25 have 63.2% power to detect a difference of 0.1 in the AUCs (.8 vs .9) and 88.7% power to detect a difference of 0.15 (0.8 vs 0.95).

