#### 1.6 Contrast Enhanced Ultrasound

CEUS has several features that distinguish it from contrast CT/MRI. Unlike contrast CT/MRI, CEUS captures real-time images, enabling dynamic visualization of contrast over time. In addition, the CEUS contrast agent, microbubbles, remains intravascular, and is thus sensitive to lesion enhancement and small vessel involvement, giving CEUS the potential to inform kidney mass staging and surgical planning, capabilities not currently possessed by CT/MRI.

In addition, CEUS microbubbles differ from CT/MRI contrast agents in that they are cleared by the lungs within minutes of administration and have no known nephrotoxicity, making CEUS safe for patients with advanced CKD. For these individuals, CEUS availability would mean access to contrastenhanced imaging, which would significantly improve the ability to provide a definitive mass diagnosis and increase the chance of avoiding unnecessary surgery. CEUS maintains the advantages of conventional US (lower cost in comparison to CT/MRI and safety).

To-date, most CEUS research has utilized a 2D approach. By adapting routine imaging techniques, we can generate three-dimensional (3D) CEUS images. Our preliminary work suggests that expanding 2D CEUS to a 3D technique will provide deeper data about mass enhancement, facilitating subtype differentiation. Moreover, our group has developed image analysis techniques that can generate 3D renderings of the vasculature (described below).

In 2D or 3D CEUS, microbubbles can be administered by bolus or continuous infusion dosing which correspond with low mechanical index (MI) and flash-replenishment imaging (F-R), respectively. The two approaches yield different information. The optimal approach is unknown.

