# 7.0 STATISTICAL CONSIDERATIONS

#### 7.1 Sample Size and Accrual

We will enroll 25 adult subjects with suspected with suspected kidney cancer and planned surgical nephrectomy. We have deep recruitment experience for kidney CEUS imaging. Approximately 150 nephrectomies for localized disease are performed at UNC yearly. Based on our previous recruitment rate of ~75% and a strong partnership with our urology colleagues, we anticipate no problems meeting our recruitment goal of 25 subjects.

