#### 7.1.1 Primary Objective

# 7.1.1.1 Predicting kidney mass diagnosis using 3D CEUS generated metrics.

The proposed sample of 25, assuming 60% clear cell legions, achieves 63.2% power to detect a difference of 0.1000 between a diagnostic test with an area under the ROC curve (AUC) of 0.8000 and another diagnostic test with an AUC of 0.9000 using a two-sided z-test at a significance level of 0.050. The correlation between the two diagnostic tests is assumed to be 0.9 for the positive group and 0.9 for the negative group.

The proposed sample of 25, assuming 60% clear cell legions, achieves 88.7% power to detect a difference of 0.1500 between a diagnostic test with an area under the ROC curve (AUC) of 0.8000 and another diagnostic test with an AUC of 0.9500 using a two-sided z-test at a significance level of 0.050. The correlation between the two diagnostic tests is assumed to be 0.9 for the positive group and 0.9 for the negative group.

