# 7.2.2 Comparing diagnostic accuracy of F-R infusion imaging technique to low MI bolus imaging technique.

Image Analysis (Flash-Replenishment TIC analysis): For each 0.5-1 cm step, we will produce a TIC by delineating an ROI of the entire mass and measuring the mean contrast signal intensity over the time course of the F-R. We will model TIC using a mono-exponential equation, UI=A(1 -  $e^{-\beta t}$ ), where UI is ultrasound intensity and  $\beta$ , the slope of the tangent to the curve, represents the rate of perfusion. The height of the curve, A, represents the perfusion volume. To produce a single value for  $\beta$  for the entire tumor volume, we will calculate a weighted average based on the ROI area of the mass at each step. This value will serve as the WI rate.

Gold Standard Comparator: Histologic diagnosis from pathologic tissue.

*Statistical Analysis:* We will follow the model building and evaluation strategy used for the primary objective. This will be done separately for bolus and infusion imaging modalities, as well as combining the two multiparametric scores. We will compare AUCs from final logistic regression models obtained for bolus and infusion using a Z-test at alpha=0.05, with standard errors obtained by bootstrapping correctly adjusting for the fact that the two AUCs are calculated using the same data and hence correlated. We will conduct similar tests comparing the AUC based on the combined model to those based on bolus and infusion multiparametric scores separately. The proposed tests with sample size 25 have 80% power to detect a difference of .1 in the AUCs (0.8 vs 0.9) and 90% power to detect a difference of 0.15 (0.8 vs 0.95).

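### The plan gives two conflicting power statements for the bolus versus infusion AUC comparison (63.2%/88.7% and 80%/90%), and the planned z-test at 15 versus 10 patients delivers neither: about 30%/57% for fixed binormal scores

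*Combined protocol and SAP*

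**What the plan says.** Section 7.1 fixes the sample size: "We will enroll 25 adult subjects". Section 7.1.1.1 gives the inputs to the power calculation: "assuming 60% clear cell legions", a two-sided z-test at 0.05, and AUCs of 0.80 versus 0.90 and 0.80 versus 0.95. On dependence it says: "The correlation between the two diagnostic tests is assumed to be 0.9 for the positive group", with the same value for the negative group. It reports 63.2% power for the smaller difference and says that the sample "achieves 88.7% power to detect a difference of 0.1500".

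Section 7.1.2.1 carries the same two figures over to the bolus versus infusion comparison: "The proposed tests with sample size 25 have 63.2% power to detect a difference of 0.1 in the AUCs", and 88.7% for a difference of 0.15. It restates no inputs, so those of 7.1.1.1 are taken to apply.

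Section 7.2.2 specifies the test: a Z-test at alpha 0.05 on the AUCs of the final bolus and infusion logistic models, "with standard errors obtained by bootstrapping" that allow for the shared patients. It follows the model evaluation strategy of section 7.2.1, which uses nonparametric AUC estimates. Section 7.2.2 then states 80% power for 0.8 versus 0.9 and 90% for 0.8 versus 0.95, again with 25 patients.

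**The concern.** One comparison has two power statements, 16.8 points apart for the smaller difference (80 − 63.2) and 1.3 points apart for the larger (90 − 88.7). Correcting one to match the other would settle the matter only if one of them described the planned test.

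That is doubtful. With 15 and 10 patients the empirical AUC moves in steps of 1/150. At 0.90 or 0.95 it lies near its ceiling, and the standard error is itself estimated from very few patients. A large-sample formula can be well off in that setting, and the plan reports no small-sample check.

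Comparing the two techniques is one of the study's two aims in section 1.2 and is secondary objective 2.2.1. If power is much lower than stated, a non-significant result says little about whether the techniques differ.

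**Working it through.** **Inputs.** N = 25 (7.1). 60% clear cell, so 0.60 × 25 = 15 positive and 10 negative (7.1.1.1). Two-sided alpha 0.05 and correlation 0.9 in each group (7.1.1.1). Empirical AUCs (7.2.1, carried into 7.2.2). Z-test with bootstrap standard error (7.2.2). The plan states no score distribution. Binormal with equal SDs is assumed here, and the SD ratio (negative to positive) is then varied over 0.7 and 1.4.

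**Step 1: reproduce the stated figures.** Power = Φ((δ − 1.96·SE0)/SE1). SE0 is the standard error of the difference with both AUCs at 0.8, and SE1 is that under the alternative. The Hanley–McNeil variance is

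Var(A) = [A(1−A) + 14(Q1−A²) + 9(Q2−A²)]/150, with Q1 = A/(2−A) and Q2 = 2A²/(1+A).

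This gives SE(0.80) = 0.0884, SE(0.90) = 0.0626 and SE(0.95) = 0.0438. The correlation between the AUC *estimates* is set at 0.88. A large-sample simulation with score correlation 0.9 and both AUCs at 0.8 gave 0.886, so 0.88 is compatible with the stated 0.9.

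- SE0 = √(2 × 0.0884² × 0.12) = 0.0433.
- 0.80 vs 0.90: SE1 = √(0.0884² + 0.0626² − 2 × 0.88 × 0.0884 × 0.0626) = 0.0447. Power = Φ((0.10 − 0.0849)/0.0447) = Φ(0.34) = 63.2%.
- 0.80 vs 0.95: SE1 = 0.0541 by the same formula. Power = Φ((0.15 − 0.0849)/0.0541) = Φ(1.20) = 88.6%.

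Obuchowski–McClish binormal variances with correlation 0.9 give 65.2% and 87.5%. So 63.2%/88.7% is a large-sample, two-sided result. One-sided versions give about 74–75% and 92–93%, which match neither that pair nor the 80%/90% of section 7.2.2.

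**Step 2: use the standard error that the planned test uses.** The bootstrap estimates the standard error from the observed data, so under the alternative it targets SE1, not SE0. Power is then Φ(δ/SE1 − 1.96). With the values above this is Φ(0.28) = 61% and Φ(0.81) = 79%. Across the two variance formulas it is about 58–61% and 72–79%. This part of the loss is asymptotic and has nothing to do with small numbers.

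**Step 3: simulate the planned test at 15 versus 10.** Correlation 0.9, equal SDs, empirical AUCs, rejection at |z| > 1.96, 10,000 trials, 500 bootstrap draws:

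| Standard error | 0.80 vs 0.90 | 0.80 vs 0.95 | Size, both AUCs 0.80 |
|---|---|---|---|
| Stated, 7.1.2.1 | 63.2% | 88.7% | 5% nominal |
| Stated, 7.2.2 | 80% | 90% | 5% nominal |
| Bootstrap, stratified | 30.2% | 57.4% | 1.5% |
| Bootstrap, unstratified | 27.0% | 53.5% | 1.1% |
| DeLong | 33.0% | 57.9% | 2.1% |

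A separate run of 1,500 trials gave 29.0% and 56.8% with the bootstrap. Letting the case mix vary at random around 60% gives 31.4% and 55.7% (DeLong).

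**Step 4: sensitivity.** SD ratios of 0.7 and 1.4, across the three standard errors, give about 24–35% and 48–61%. At correlation 0.7, DeLong gives 19.0% and 42.1%. At correlation 0.5, the bootstrap gives 16.2% and 36.1% and DeLong 15.1% and 34.2%.

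**Step 5: split the shortfall.** It totals 63.2 − 30.2 = 33.0 points and 88.7 − 57.4 = 31.3 points. Step 2 explains about 2–5 points of the first (63.2 less 58–61) and about 10–17 of the second (88.7 less 72–79). The remainder is the conservatism and discreteness of the z-test at this sample size.

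**The case against.** **The stated figures are not miscalculated.** Section 7.1.1.1 gives its inputs, and a standard formula returns its numbers. This stands. The fault is that the formula does not describe the planned test at this sample size, and that section 7.2.2 reports different numbers.

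**The result depends on the test.** A percentile bootstrap interval with empirical AUCs gives 48.4% and 75.9%. A parametric binormal AUC with bootstrap z gives 60.4% and 84.5%, close to the first stated pair. Section 7.2.2 specifies neither. That it inherits the nonparametric AUC from 7.2.1 is an inference, though a natural one.

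**The simulation is not the full planned procedure.** Section 7.2.2 compares fitted, selected logistic models, while the simulation takes each technique as one fixed score. A reader might infer that in-sample fitting can only lower power further, or that the test will be conservative in practice. Neither follows. In a check of 1,500 runs, with an assumed five noise predictors added to bolus and one to infusion and no selection, rejection at equal true AUCs of 0.8 rose from 1.8% to 6.6%. It was 34% when bolus was truly better by 0.1 and 1.4% when infusion was. Fitting can therefore favour the technique with more predictors.

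**The correlation of 0.9 is not contradicted.** Section 1.6 says "The two approaches yield different information", which might be read as ruling out so high a value. It is a qualitative remark. Both techniques image the same mass, and both models may include the same B-mode and patient factors. The values 0.5 and 0.7 are sensitivity assumptions.

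**Misuse of a null result is not planned.** Nothing in the documents says that a non-significant difference will be read as similarity. That is a risk of interpretation only.

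**Conclusion.** The point holds for the bolus versus infusion comparison. Sections 7.1.2.1 and 7.2.2 contradict each other, which needs no simulation to see, and neither pair describes the planned test. At correlation 0.9 the power is about 30% for a difference of 0.1, roughly half of the lower stated figure, and about 57% for 0.15, some 31 points below it. The corresponding miss rates are about 70% and 43%. No standard error or SD ratio examined brings the planned z-test near either stated pair.

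This rests on binormal scores, fixed scores for each technique, empirical AUCs and exactly 15 versus 10 patients. The 30% and 57% should therefore not be read as the exact power of the planned procedure, nor the size of 1.5–2% as the size of the test on fitted models.

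Because section 7.1.1.1 prints the same figures, a reader might also carry 30% and 57% over to the primary objective. The documents do not support that. The primary test in section 7.2.1 is a one-sided test of a single final-model AUC against 0.8, so a paired two-sided calculation does not give its power.

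**What to change.** - In sections 7.1.2.1 and 7.2.2, replace both pairs of figures with one simulated pair for the planned test: about 30% and 57% at correlation 0.9. Label it as fixed scores, binormal, with model fitting and selection not modelled.
- Beside it, show the range for correlations 0.5 to 0.9 (about 16% and 35% at 0.5), and state the score distribution and the bootstrap scheme assumed.
- Present the comparison mainly as an estimated AUC difference with a 95% confidence interval. Section 7.1.2.2 already takes this line for staging, where it concedes that power is insufficient and turns to estimation.
- Do not enter these paired figures in section 7.1.1.1. Give that section its own power statement for the one-sided single-AUC test in section 7.2.1.

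The cost is a text change, with no extra patients or procedures. The stated power becomes less favourable.

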#### 7.1.2.2 To predict kidney mass stage using 3D CEUS-generated metrics

Based on our clinical experience, we estimate 15 patients will have a T2a category or lower lesion and 25% of those will have a change from clinical to pathological staging. A sample size of 15 patients will not have sufficient power to detect areasonable effect size but computation of parameter estimates and standard errors will inform larger future studies.

#### 7.2 Data Analysis Plans

#### 7.2.1 Predicting kidney mass diagnosis using 3D CEUS generated metrics.

*Image Analysis (Low MI TIC analysis):* We will use Matlab (Mathworks, Natick, MA) for time intensity curve (TIC) analysis and 3D volume rendering. For each imaging plane, we will create a region of interest (ROI) by delineating the entire mass in the image slice. We will produce a TIC by taking the mean signal intensity in the ROI at each time point and calculate the metrics of wash-in rate (WI), wash-out rate (WO), mean transit time (MTT), time to peak (TTP) and peak enhancement relative to the surrounding parenchyma (PE) for each x-sweep position. A weighted average based on the ROI area at each position will be used to produce single values for the 3D volume for each TIC metric (WI, WO, MTT, TTP and PE). We will repeat this process for each plane of imaging.

3D volume rendering: We will also create 3D renderings of the tumor vasculature from the CEUS images. We will sort the image data collected over the 3-minute period after a bolus injection by the x- (or y-) sweep position, then by capture time in relation to the start of bolus injection through the wash-out period. We will produce a cumulative contrast image (CCI) at each position with the time-dependent image data by summing all time-dependent image data at each position. The images show where the microbubbles have travelled throughout the acquisition period, and since microbubbles are confined to the vascular spaces, the images provide excellent delineation of the vasculature. We will stack the CCIs together to create a 3D rendering.

Multiparametric score and statistical analysis: We will combine the

Table 1. Factors to be used in multiparametric score					
CEUS factors	B-mode factors	Patient factors			
WI, WO, MTT,	Length,	Age, sex, race			
TTP, PE, total	echogenicity,				
volume	shape				

quantitative data derived from CEUS image analyses into a single score. For the primary analysis using the gold

standard of histologic diagnosis to differentiate clear cell from non-clear cell tumors, we will use logistic regression to build predictive models based on multiple parameters from CEUS (WI, WO, MTT, TTP, PE and tumor volume), B-mode US images (length, echogenicity, shape), as well as patient factors (age, sex, race) (Table 1). We will assess the effects of individual parameters using hypothesis tests based on parameter estimates from the fitted logistic regression model. This approach facilitates assessment of the added value of the CEUS measurements over other patient factors. We will calculate nonparametric estimates and 95% confidence intervals for area under the curve (AUC) using the fitted logistic regression models, both with and without non-CEUS patient factors. We will use model selection procedures, including AUC, to identify a final model, with a one-sided test of AUC  $\leq .8$  vs AUC  $\geq .8$  at alpha=.05 for the final model. We will use model selection procedures based on optimizing AUC to identify a final model, with a one-sided test of AUC<=0.8 vs AUC>=.8 at alpha=.05 for the final model.

Gold Standard Comparator: Histologic diagnosis from pathologic tissue.

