#### 1.3 Kidney Cancer Histologic Subtypes

The majority of kidney cancers are renal cell carcinomas (RCC) of which there are three main subtypes: clear cell, papillary and chromophobe. The subtypes differ in incidence, prognosis[8, 9] and vascularity[10]. Accurate subtyping is critical to clinical decision-making as less aggressive subtypes do not require immediate resection. Differentiation of clear cell (a higher risk subtype requiring resection) from other subtypes or benign kidney masses has the potential to reduce unnecessary surgeries[6]. CT/MRI, the predominant imaging modalities used to diagnose RCC, do not reliably predict cancer subtype or grade. Other than surgical resection, biopsy is the only reliable way to preoperatively determine histologic subtype and tumor grade. However, biopsy is not performed at all centers[11] and is subject to sampling error, with as many as 20% of biopsies being non-diagnostic[12].

Differences in tissue vascularity cause differing tissue enhancement[13]. CEUS is highly sensitive for tissue enhancement which can be leveraged to differentiate kidney mass subtype based on enhancement properties. Previous studies have reported accurate diagnosis[14] and subtyping[15] of kidney masses using single plane CEUS with qualitative interpretations. 3D CEUS-generated metrics will capture enhancement in multiple planes and thus produce a more complete picture of the entire mass. Specifically, we will use 3D CEUS-generated quantitative metrics to characterize mass vascularity.

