#### 4.2.2 Imaging Procedures

#### 4.2.2.1 Low MI imaging with sweeps

Upon subject arrival, a urine pregnancy test will be conducted for subjects with child bearing potential. Once confirmed that a subject is eligible, a nurse will place an intravenous (IV) catheter, and a sonographer will determine mass location and approach with a baseline B-mode US. The nurse will prepare the CEUS contrast agent, Definity®, to be administered via infusion pump according to package insert instructions. We will use a Siemens ACUSON Sequoia S512 with a 4C1 curved array transducer equipped with cadence pulse sequencing technology for contrast-enhanced imaging.

Each subject will be injected with a bolus of 0.2-0.4 mL undiluted microbubbles placed on an infusion pump for consistent injection rate and followed by 5mL sterile saline. The sonographer will capture sweeps through the kidney in 2-3 different planes (i.e. x-y, y-z, or x-z) of imaging during contrast infusion. Each imaging plane will require a new bolus. During imaging, the subject will be instructed to take shallow breaths to minimize movement artifact. We will capture a B-mode image perpendicular to each sweep direction to determine the total length of each sweep. The subject will be instructed to take shallow breaths to minimize movement artifact. Imaging time will be 15-20 minutes.

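### Tumour volume is classed as a CEUS factor, so no planned AUC separates the contrast-derived metrics from tumour size

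*Combined protocol and SAP*

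**What the plan says.** Section 7.2.1 combines the image measurements into one score, with the inputs listed under "Table 1. Factors to be used in multiparametric score". The CEUS column holds WI, WO, MTT, TTP, PE and total volume. The B-mode column holds length, echogenicity and shape, and the patient column holds age, sex and race. The analysis text repeats the grouping: "multiple parameters from CEUS (WI, WO, MTT, TTP, PE and tumor volume), B-mode US images (length, echogenicity, shape").

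The same section derives only five quantities from the time-intensity curve. Area-weighted averaging is used "to produce single values for the 3D volume for each TIC metric (WI, WO, MTT, TTP and PE"). The only outline of the mass that it describes is geometric: "we will create a region of interest (ROI) by delineating the entire mass in the image slice". Section 1.3 gives the purpose of the metrics: "we will use 3D CEUS-generated quantitative metrics to characterize mass vascularity".

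AUCs are to be estimated "using the fitted logistic regression models, both with and without non-CEUS patient factors". Of the modelling as a whole, the plan says: "This approach facilitates assessment of the added value of the CEUS measurements over other patient factors". Section 2.3 makes the primary endpoint the 3D CEUS metric or metrics that best predict the pathological diagnosis.

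**The concern.** Length and volume both describe how large the mass is. Filing one under B-mode and the other under CEUS means that predictive information carried by size is credited partly to contrast imaging. Size can be known without injecting contrast. The case for CEUS in Section 1.3 rests on vascularity.

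Three outputs are exposed: the AUCs, the naming of the best 3D CEUS metric, and the statement of added value. The trial could report that CEUS metrics distinguish clear cell from other masses when much of the discrimination came from size. Section 7.2.2 reuses the modelling strategy for bolus and infusion, so the grouping carries over there. Section 7.2.3 uses only WI and WO as its CEUS predictors of stage and is not affected.

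**Working it through.** **The plan's own figure.** Section 7.1.1.1 gives 63.2% power (AUC 0.8 v 0.9) and 88.7% (0.8 v 0.95), with 25 subjects, 60% clear cell (15 v 10), two-sided alpha 0.05 and correlation 0.9. The Hanley-McNeil variance is V(A) = [A(1−A) + 14(Q1−A²) + 9(Q2−A²)]/150, with Q1 = A/(2−A) and Q2 = 2A²/(1+A).

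- V(0.8) = 0.00782, V(0.9) = 0.00392, V(0.95) = 0.00192.
- With an AUC correlation of 0.88 (an assumed conversion of the 0.9 rating correlation), the null SE is √(2 × 0.00782 × 0.12) = 0.0433. The alternative SEs are 0.0447 and 0.0541.
- Power is Φ[(0.10 − 1.96 × 0.0433)/0.0447] = 63.2% and Φ[(0.15 − 1.96 × 0.0433)/0.0541] = 88.6%.

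A binormal covariance with 0.9 used directly gives 65.2% and 87.5%. The stated power is reproduced to within about 2 points, and the present point does not depend on it.

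**Which factors are in which AUC.** The phrase about non-CEUS patient factors has two readings.

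| Factors | Table 1 column | Kept if only age, sex, race are dropped | Kept if B-mode is dropped too |
|---|---|---|---|
| WI, WO, MTT, TTP, PE | CEUS | yes | yes |
| Volume | CEUS | yes | yes |
| Length | B-mode | yes | no |
| Echogenicity, shape | B-mode | yes | no |
| Age, sex, race | Patient | no | no |

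The first reading is the more natural, since Table 1 has a column for patient factors. Size remains in both AUCs either way: as volume and length on the first reading, as volume on the second. No baseline of size or B-mode factors alone is named.

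**How much size could add.** The documents give no size difference by histology, so d2, the difference in log size in SD units, is an assumption. For independent normal predictors, size alone has AUC = Φ(d2/√2), and the combination has AUC = Φ(√(d1² + d2²)/√2). An assumed enhancement AUC of 0.75 gives d1 = √2 × 0.6745 = 0.954.

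| d2 (SD) | Size alone | Enhancement plus size |
|---|---|---|
| 0.3 | 0.58 | 0.76 |
| 0.5 | 0.64 | 0.78 |
| 0.8 | 0.71 | 0.81 |
| 1.0 | 0.76 | 0.84 |

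Reaching 0.80 from 0.75 needs d2 = √[(√2 × 0.8416)² − 0.954²] = 0.71 SD. From an enhancement AUC of 0.70, a 0.8 SD difference reaches only 0.78. From 0.65, a 1.0 SD difference reaches only 0.79.

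**Chance that volume is the best single CEUS metric.** Simulated trials of 15 v 10, each AUC taken in its better direction, d2 = 0.3, 0.5, 0.8, 1.0:

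- All five contrast metrics uninformative: 24%, 36%, 60%, 73% (17% if volume is uninformative too).
- One contrast metric with true AUC 0.75: about 10%, 18%, 35%, 50%.

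**Apparent AUC of a fitted six-factor block.** With five uninformative contrast metrics and volume at a true AUC of 0.70, the mean apparent AUC is 0.84 with volume and 0.75 without (2,000 runs). With volume uninformative the pair is 0.78 and 0.76, so about 0.03 of the gap is overfitting from a sixth parameter. Even without volume, 28–29% of runs exceed 0.8. That is overfitting, and reclassifying volume does not address it.

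**The case against.** **The plan tests individual parameters, and a named winner would be visible.** Section 7.2.1 tests coefficients in a model that can include length. If volume won outright, the report would say so and a reader would recognise it as size. This stands in part. It does not separate the AUC of a combined score. Length and volume are also strongly collinear: assuming log-normal sizes with 10–20% shape or measurement noise, the correlation is 0.93–0.98 and the variance inflation about 7 to 26. The tests are therefore weak with 25 subjects.

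**A volume measured from 3D CEUS sweeps is literally a CEUS-generated metric.** Grouping by source of acquisition is defensible, but it does not serve the purpose stated in Section 1.3.

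**Volume may mean something else.** Table 1 says total volume, the text says tumor volume, and neither is defined. The vessel rendering is described just before Table 1, so a contrast-filled vascular volume is possible, and that would need contrast. This stands as a reason to define the term. The text's wording favours mass size, and Section 7.2.2 uses a separate term, perfusion volume, for the contrast quantity. A reader might also infer that volume takes its scale from B-mode because of "We will capture a B-mode image perpendicular to each sweep direction to determine the total length of each sweep", but the documents never link that step to volume.

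**The formal test is untouched.** This stands in full. The one-sided test against 0.8 applies to a final model selected from all the factors, and moving volume between columns leaves that pool unchanged.

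**Conclusion.** The point holds as one of interpretation. As grouped, the plan cannot separate contrast information from tumour size in its AUCs, its endpoint metric or its statement of added value.

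Two stronger readings are tempting and the documents do not support them. One is that the plan reports an AUC for CEUS alone that size inflates. On the more natural reading no such AUC is planned, and B-mode length stays in as well. The other is that the grouping could carry the primary test past 0.8. That test is not assigned to the CEUS block. Even for that block, crossing 0.8 needs an enhancement AUC near 0.75 together with a size difference of at least about 0.71 SD, both of them assumptions.

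The magnitude is unknown. From an enhancement AUC of 0.75, size adds 0.01 to 0.09 over 0.3 to 1.0 SD, if size and enhancement are independent normal predictors. This is a low-cost improvement, not a flaw that invalidates the analysis.

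**What to change.** - Define volume in Section 7.2.1 and use one term for it. If it is the volume of the mass, list it as a size variable with the B-mode factors and keep either length or volume. If a contrast-filled vascular volume was meant, say so, describe how it is measured, and keep it under CEUS.
- Report an AUC with 95% confidence interval for WI, WO, MTT, TTP and PE without any size variable.
- Report the change in AUC when those five metrics are added to a model of size, B-mode and patient factors.
- Base the Section 2.3 endpoint and the added-value statement on those metrics, together with vascular volume if that is what was meant. State which factors are dropped in the AUC without non-CEUS patient factors.

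The cost is a table entry, a few sentences and slightly more analysis of data already collected. Sample size, imaging and stated power do not change, and size remains available to the full model. The AUC credited to CEUS may come out lower.

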#### 2.3 Endpoints

The primary study endpoint will be 3D CEUS generated metric(s) that best predict kidney mass diagnosis based on pathologic examination.

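### The planned tests of individual CEUS metrics, read as Wald tests on logistic coefficients, lose power for strong metrics at N = 25 and are close to unusable with all twelve factors

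*Combined protocol and SAP*

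**What the plan says.** Section 2.3 defines the endpoint at the level of metrics: "The primary study endpoint will be 3D CEUS generated metric(s) that best predict kidney mass diagnosis based on pathologic examination".

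Section 7.2.1 fits logistic models for clear cell versus non-clear cell histology from "multiple parameters from CEUS (WI, WO, MTT, TTP, PE and tumor volume), B-mode US images (length, echogenicity, shape), as well as patient factors (age, sex," and race. That is 6 CEUS + 3 B-mode + 3 patient factors = 12 candidates (Table 1), and more than 12 coefficients if echogenicity, shape or race has more than two categories. For single factors it says "We will assess the effects of individual parameters using hypothesis tests based on parameter estimates from the fitted logistic regression model", and adds that this approach helps to show what CEUS contributes beyond patient factors. It gives no alpha for these tests, no named test statistic, and no rule for separated data.

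The same section also reports nonparametric AUCs with confidence intervals for the fitted models, with and without non-CEUS patient factors. It chooses a final model by optimising AUC and tests that model's AUC one-sided against 0.8.

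On size, section 7.1 says "We will enroll 25 adult subjects". Section 7.1.1.1 assumes 60% clear cell and gives power for AUC 0.80 versus 0.90 and 0.80 versus 0.95.

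**The concern.** A test built from a parameter estimate is, on the ordinary reading, the estimate divided by its standard error, that is, a Wald test. In a small logistic regression the standard error can grow faster than the coefficient as a predictor approaches perfect discrimination (the Hauck-Donner effect). The Wald statistic then shrinks although the evidence is stronger. Under complete separation, finite maximum-likelihood estimates do not exist and the Wald p-value has no meaning.

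Two readings are at stake: whether a given CEUS metric is reported as related to histology, and whether CEUS adds anything beyond patient factors. With 25 patients and up to twelve factors, both could come out negative because of the test rather than the data.

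**Working it through.** **Inputs.** N = 25 (7.1). Clear cell 60%, so 0.60 × 25 = 15 versus 10 (7.1.1.1). Twelve candidate factors (7.2.1, Table 1). Design AUCs 0.80, 0.90 and 0.95 (7.1.1.1). Assumed, because the plan is silent: two-sided alpha 0.05 for the coefficient tests, and normally distributed metrics with equal variance in the two groups.

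**The plan's own power figures.** They concern a comparison of two correlated AUCs, not the coefficient tests, but they confirm the 15/10 design. Take the binormal variance with equal variances, R = 10/15, r = 0.9, A = √2·Φ⁻¹(AUC), f = exp(−A²/4)/√(4π) and g = −A·exp(−A²/4)/√(16π):

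- V = f²(1 + 1/R + A²/2) + g²(1 + R)/(2R) + f·g·A
- C = f₁f₂(r + r/R + r²A₁A₂/2) + g₁g₂·r²(1 + R)/(2R) + (r²/2)(f₁g₂A₁ + f₂g₁A₂)
- Variance of the difference = V₁ + V₂ − 2C, called V0 when both AUCs are 0.80 and VA under the alternative
- Power = Φ[(Δ√15 − 1.96√V0)/√VA]

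For 0.80 versus 0.90: V0 = 0.0262 and VA = 0.0323, so power = Φ[(0.387 − 0.317)/0.180] = Φ(0.39) = 65.2%. The plan has 63.2%.

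For 0.80 versus 0.95: VA = 0.0524, so power = Φ[(0.581 − 0.317)/0.229] = Φ(1.15) = 87.5%. The plan has 88.7%.

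Both agree within 2 points. The plan gives no power for the coefficient tests.

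**Simulating the coefficient tests.** In each replicate, 15 versus 10 patients are drawn and the informative metric is shifted by √2·Φ⁻¹(AUC) in the clear cell group. The other factors are noise. The logistic model is fitted by maximum likelihood and the metric is called significant if |estimate/SE| > 1.96. Ranges are across independent runs of 300 to 4,000 replicates. Monte Carlo error is about 1 to 3 points.

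| True AUC of the metric | 0.70 | 0.80 | 0.85 | 0.90 | 0.95 | 0.98 |
|---|---|---|---|---|---|---|
| Wald, metric alone | 32% | 71–73% | 85–86% | 88–89% | 70–72% | 40–42% |
| Wald, with 5 noise factors | 19–22% | 33–36% | 32–36% | 25–30% | 9–13% | 2–3% |
| Wald, all 12 factors | 2% | 1–2% | 1% | ≤2% | ≤2% | not run |

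If the six metrics are correlated at 0.5, the Wald figures at AUC 0.70, 0.80, 0.90 and 0.95 are 31%, 31%, 9% and 2%.

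**Separation.** With 12 factors plus an intercept and 25 patients, Cover's count gives the probability that randomly assigned labels are linearly separable: Σ C(24,k) for k = 0 to 12, divided by 2²⁴, = 9,740,686 / 16,777,216 = 0.58. Simulation at 15 versus 10 with no signal gives 0.56 to 0.61. With one informative metric among the twelve, separation occurs in about 87%, 97% and 99.7% of samples at AUC 0.80, 0.90 and 0.95. With six factors the figures are 14%, 43% and 75%.

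**The information is in the data.** Firth-penalised likelihood-ratio tests under the same design give:

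| Power at true AUC | 0.80 | 0.90 | 0.95 |
|---|---|---|---|
| Firth, metric alone | 79–82% | 99% | 100% |
| Firth, six factors | 65–68% | 93–96% | 99% |
| Firth, twelve factors | 33–43% | 59–64% | 75–77% |

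Type I error is about 2% to 6%. The ordinary likelihood-ratio test also keeps its power, but its type I error is about 11–12% with six factors and 23% with twelve, so it is not a safe substitute.

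**An illustration of what a reader would see.** Put one metric at AUC 0.95 and five at 0.75, each tested alone. The best metric has the largest Wald statistic in 36% of trials and the largest AUC in 91%. In 29% it is non-significant while a weaker metric is significant.

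**The case against.** The strongest reply is that the primary endpoint is not decided by these tests. Section 7.2.1 picks the final model by optimising AUC and tests that model's AUC against 0.8. It states no rule that ranks, keeps or drops a metric by its p-value. That stands: a reader might infer that the best metric would be removed from the model or lose the endpoint, and the documents do not support it. The whole-model AUC test does not, however, say which metric predicts best. The coefficient tests are the only named tests of individual metrics, and 7.2.1 plans no AUC for each metric on its own.

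Second, one might infer that power falls generally as a metric improves. It does not. Tested alone, Wald power rises up to AUC about 0.90, and 0.95 is level with 0.80. The turn comes earlier, at about 0.70 to 0.85, only with several factors in the model.

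Third, the AUCs of 0.90 and 0.95 in 7.1.1.1 describe a whole diagnostic test, and nothing in the plan assumes that a single metric reaches 0.95. That also stands. But even at AUC 0.80 in a six-factor model, Wald power is about 34% against 65–68% for the penalised test.

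Fourth, with all twelve factors the trouble is separation and overfitting, not strong metrics in particular. Agreed; the planned tests are near unusable there for any metric.

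Finally, the plan never uses the name Wald. That reading is inferred from its wording; if another test is meant, the plan should say so.

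**Conclusion.** The point holds in limited form and should be fixed. If the individual-parameter tests are Wald tests, their power at 15 versus 10 drops from about 88% at AUC 0.90 to about 71% at 0.95 for a metric tested alone. It goes from about 34% at 0.80 to 10% at 0.95 with five noise factors, and is about 2% or less with all twelve. A strong CEUS metric, or the contribution of CEUS beyond patient factors, can thus be reported as non-significant when the data show it clearly.

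The documents do not support the stronger claim that the primary endpoint is judged by these tests, because AUC governs both the choice and the test of the final model. The sizes rest on normal, equal-variance metrics, two-sided 0.05, the planned 60% clear cell share, and noise for the remaining factors.

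**What to change.** In section 7.2.1:

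1. Replace the coefficient tests with Firth-penalised likelihood-ratio tests, or permutation tests, and state the alpha. The Firth fit also gives finite estimates under separation, so it can serve as the stated rule for separated data.
2. Report the AUC with 95% CI for each of the six CEUS factors on its own (WI, WO, MTT, TTP, PE and tumor volume), as section 7.2.3 already does for WI and WO from fitted models.
3. Base the statement of which metrics predict best on those six AUCs and their intervals, not on coefficient p-values.

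The penalised test does not make a twelve-factor model well powered: at AUC 0.80 its power there is still only about 33–43%, and the report should say so. The cost is a change of wording and slightly more analysis work with standard software. No new data or patients are needed.
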